### *Infectivity*

1. To determine the peak titer of vaccine virus shed and duration of virus shedding by each participant
2. To assess the proportion of vaccinated participants infected with study vaccine (If < 70% of RSV-seronegative vaccinees are infected with vaccine virus, the study product will be considered over-attenuated.)

### *Immunogenicity*

1. To characterize serum antibody responses to the study product 28 days after inoculation of RSV-seropositive vaccine recipients (group 1)

2. To characterize serum antibody responses to the study product 56 days after inoculation of RSV-seronegative vaccine recipients (group 2)

## **2.2. SECONDARY OBJECTIVES**

1. To characterize the frequency and severity of symptomatic medically attended respiratory and febrile illness in RSV-seronegative vaccine and placebo recipients (group 2) who experience natural infection with wt RSV during the subsequent RSV season(s)
2. To characterize serum antibody responses in RSV-seronegative vaccine and placebo recipients (group 2) who experience natural infection with wt RSV during the subsequent RSV season(s)
3. To characterize mucosal antibody responses to vaccine in RSV-seropositive (group 1) and RSV-seronegative (group 2) participants

## **2.3. EXPLORATORY OBJECTIVE**

Study samples may be used in comparative assays with samples from other RSV vaccine studies initiated by the LID, NIAID, NIH.

## **3 STUDY DESIGN**

The study will be double-blind, randomized, and placebo-controlled. Participants in groups 1 and 2 will be block-randomized in groups of 3 at a ratio of 2:1 to receive vaccine or placebo, respectively. The vaccine will be evaluated in a stepwise fashion beginning with RSV-seropositive children (Group 1) and proceeding sequentially in RSV-seronegative children (Group 2). For the purpose of this study, RSV-seropositive is defined as having a serum neutralizing antibody titer of  $\geq 1:40$ , and RSV-seronegative is defined as having a serum neutralizing antibody titer of  $< 1:40$ . This definition has been used in previous evaluations of live-attenuated RSV vaccines (11, 24, 35). In these previous studies, live-attenuated RSV vaccines were highly restricted in replication and poorly immunogenic in children with titers  $\geq 1:40$  but were far less restricted in replication and highly immunogenic in children with titers  $< 1:40$ . These data suggest that this neutralizing antibody cutoff can distinguish effectively between RSV-experienced and RSV-naïve children.

The study will proceed to group 2 if there are not more than 2 vaccine-associated solicited AEs and no vaccine-associated LRIs in RSV-seropositive children. If 3 or more RSV-seropositive children have respiratory or febrile illness that coincides with shedding of  $> 10^{2.5}$  PFU of vaccine virus as detected by culture, then we will enroll an additional 15 RSV-seropositive children to continue evaluating the safety, infectivity, and immunogenicity of the vaccine virus.

Enrollment occurs at the time of inoculation with study product, Day 0, and will occur between April 1 and October 31 to avoid the time during which wt RSV typically circulates in the community ([Appendix V](#), Figure 6). Accrual will stop prior to November 1.

For group 1, RSV-seropositive participants, the duration of participation in the initial phase of the study is 28 days. The initial phase consists of an Acute Phase from inoculation through the 10th day after inoculation, and a Post-Acute Phase from the 11th day through the 28th day after inoculation. For group 2, RSV-seronegative participants, the duration of participation in the initial phase of the study is 56 days. The initial phase consists of an Acute Phase from inoculation through the 28th day after inoculation, and a Post-Acute Phase from the 29th day through the 56th day after inoculation.

During the Acute Phase, the participants' parents/guardians will be contacted daily. These contacts will consist either of an in-person evaluation of interim medical history, clinical assessment, and nasal rinse, or an interim medical history conducted by a mutually agreed upon communication method. During the Acute Phase, the participants will be evaluated for AEs or SAEs. Participants who have a febrile or respiratory illness or otitis media will have a study visit to perform a nasal rinse. The nasal rinse will be tested for RSV and for other respiratory pathogens that are considered adventitious agents. During the Post-Acute Phase, study participants' parents/guardians will be instructed to contact the study staff if any SAEs occur. The RSV-seropositive participants will have a scheduled follow-up visit on the 28th day after inoculation, and the RSV-seronegative participants will have a scheduled follow-up visit on the 56th day after inoculation. The schedules of evaluations during the Acute Phase and Post-Acute Phase are shown in Appendix II, [Table 30](#).

For the RSV-seronegative participants (group 2), the study has a third phase that assesses the incidence and severity of illness suggestive of RSV occurring during the RSV season following inoculation. During the RSV Season Surveillance Period, encompassing November 1 to March 31, study staff will make weekly contact with the participants' parents/guardians to identify medically attended episodes of fever, URI, LRI, or otitis media. Participants who have such an episode will have an in-person evaluation of interim medical history, clinical assessment, and nasal rinse to evaluate for RSV and other respiratory pathogens that are considered adventitious agents (Appendix III).

The RSV-seronegative participants will also have a study visit during the pre-RSV season between October 1 and 31 to collect a blood sample and nasal rinse sample and/or nasosorption synthetic absorptive matrix (SAM) strip for immunological assays. The samples will be used to assess the durability of the vaccine response. Participants will have a post-RSV season visit to collect blood and nasal rinse and/or nasosorption SAM strip specimens to further assess the durability of the vaccine response and to assess the immune response to naturally occurring wt RSV infection. The RSV-seronegative participants may have an overlap between the initial phases and the RSV surveillance phase of the study, depending upon the date of inoculation.

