**Table 1: Inoculation Schedule**

Group #	N	Study Product	Dose
1	10	RSV 6120/ΔNS2/1030s	$10^{5.7}$ PFU*
	5	Placebo	0
2	14-20	RSV 6120/ΔNS2/1030s	$10^{5.0}$ PFU*
	7-10	Placebo	0

\*plaque-forming units (PFU)

[figure not shown]
The study will start with group 1 and proceed to group 2 if there are not more than 2 vaccine-associated solicited adverse events (AEs) (Days 0 through 10) and no vaccine-associated lower respiratory illnesses (LRIs) (Days 0 through 28) in RSV-seropositive children. If 3 or more RSV-seropositive children (group 1) have respiratory or febrile illness that coincides with shedding of  $> 10^{2.5}$  PFU of vaccine virus as detected by culture, then we will evaluate the safety, infectivity, and immunogenicity of the vaccine virus in an additional 15 RSV-seropositive children before determining whether to continue with group 2.

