## RSV Vaccine Candidates with an NS2 Deletion

rA2cp $\Delta$ NS2 contains the NS2 deletion as well as a set of 5 amino acid substitutions in the N, F, and L proteins that were identified in a cold-passaged (cp) RSV (V267I in N; E218A and T523I in F; and C319Y and H1690Y in L) (28, 29). rA2cp248/404 $\Delta$ NS2 contains all of the mutations in rA2cp $\Delta$ NS2 as well as two additional point mutations: "248," an amino acid substitution in the L protein (Q831L) (28, 30, 31), and "404," a nucleotide substitution in the M2 gene start signal (30, 32). rA2cp530/1009 $\Delta$ NS2 also contains all of the mutations in rA2cp $\Delta$ NS2 as well as two additional point mutations in L: "530" (F521L) and "1009" (M1169V) (33, 34).

rA2cp $\Delta$ NS2, which had the fewest attenuating mutations, was evaluated in a dose-escalating study ( $10^{5.0}$  PFU,  $10^{6.0}$  PFU, or  $10^{7.0}$  PFU) administered to a total of 45 adults, and was also evaluated at a dose of  $10^{5.0}$  PFU in eight 15- to 59-month-old RSV-seropositive children. Shedding of rA2cp $\Delta$ NS2 was not detected in any of the adults, and only 2 of 16 adults who received  $10^{7.0}$  PFU had an antibody response. In contrast, at the dose of  $10^{5.0}$  PFU, rA2cp $\Delta$ NS2 was shed by 3 of 8 vaccinated seropositive children with mean peak titers of  $10^{3.4}$  PFU/mL of nasal wash. Two additional children had detectable virus by polymerase chain reaction (PCR). Based on these results, rA2cp $\Delta$ NS2 was deemed under-attenuated, and was not further evaluated in seronegative children.

rA2cp248/404 $\Delta$ NS2 was evaluated in adults (n = 16 vaccinees), 15- to 59-month-old RSV-seropositive children (n = 16 vaccinees), and 6- to 24-month-old RSV-seronegative children (n = 10 vaccinees). rA2cp248/404 $\Delta$ NS2 was not shed by adults. Only one seropositive child shed vaccine virus (peak titer of  $10^{0.4}$  PFU/mL of nasal wash), and four seronegative children shed vaccine virus (mean peak titer of  $10^{2.3}$  PFU/mL of nasal wash).

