### **1.2.3 Previous Clinical Experience**

The live-attenuated recombinant RSV 6120/ΔNS2/1030s vaccine virus is being evaluated for the first time in humans. Based on preclinical data, RSV 6120/ΔNS2/1030s is expected to be more attenuated than the previously tested vaccine candidate rA2cpΔNS2, but less attenuated than the vaccine candidates rA2cp248/404ΔNS2 and rA2cp530/1009ΔNS2, which were deemed over-attenuated in seronegative infants and children, and slightly less attenuated and more immunogenic than RSVΔNS2/Δ1313/I1314L. As noted above, this vaccine is predicted to be attenuated and well tolerated in seropositive and seronegative children.

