## **1.3 RATIONALE**

## **1.4 CLINICAL DEVELOPMENT PLAN**

The investigational RSV vaccine RSV 6120/ΔNS2/1030s will be evaluated sequentially in RSV-seropositive children followed by evaluation in RSV-seronegative infants and children. The main purpose of this study is to determine whether RSV 6120/ΔNS2/1030s is well tolerated and restricted in replication in RSV-seropositive children, and well tolerated, infectious, immunogenic, and genetically stable in RSV-seronegative infants and children. If the study product is found to be well tolerated, infectious, and immunogenic in RSV-seronegative infants and children, then a safety and immunogenicity study in infants < 6 months of age will be initiated. Plans will be made in consultation with industry collaborators as a lead RSV vaccine candidate is identified.

The primary immunogenicity endpoints to be evaluated are RSV neutralizing antibody titer, and RSV F protein antibody (by ELISA). Neutralizing antibody is a well-established and important surrogate marker of effective immunity to RSV disease. Antibodies to the F protein are also associated with cross-subgroup neutralization and protection (13). These assays will be performed at the Johns Hopkins University (JHU) CIR laboratory.

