## **9.2 OUTCOME MEASURES**

### **9.2.1 Primary Outcome Measures**

*Safety: Types and grades of study product-related:*

- Solicited AEs as defined in Appendix IV from Study Days 0-10 for RSV-seropositive and Study Days 0-28 for RSV-seronegative participants
- Unsolicited AEs from Study Days 0-10 for RSV-seropositive and Study Days 0-28 for RSV-seronegative participants
- SAE (Section 8.1.2) from Study Days 0-28 for RSV-seropositive and Study Days 0-56 for RSV-seronegative participants

*Infectivity:*

- Infection with RSV as defined as
  - 1) vaccine virus identified in a nasal wash from Study Days 0-10 for RSV-seropositive and Study Days 0-28 for RSV-seronegative (a binary outcome based on nasal washes done throughout the study period; Day 0 nasal wash will be counted as baseline); or
  - 2)  $\geq 4$ -fold rise in RSV neutralizing antibody titer from Study Days 0-28 for RSV-seropositive and Study Days 0-56 for RSV-seronegative subjects
- Peak titer of vaccine virus shed from Study Days 0-10 for RSV-seropositive and Study Days 0-28 for RSV-seronegative subjects
- Duration of virus shedding in nasal washes as determined by a) culture and b) RT-PCR from Study Days 0-10 for RSV-seropositive and Study Days 0-28 for RSV-seronegative subjects

*Immunogenicity:*

- $\geq 4$ -fold rise in RSV-neutralizing antibody titer from study entry to Study Day 28 for RSV-seropositive and from study entry to Study Day 56 for RSV-seronegative subjects
- $\geq 4$ -fold rise in IgG antibody responses to RSV F glycoprotein (ELISA) from study entry to Study Day 28 for RSV-seropositive and from study entry and Study Day 56 for RSV-seronegative subjects

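### The rule for opening Group 2 counts vaccine-virus shedding only in children who are also ill, so high-titer shedding in seropositive vaccinees who stay well meets the proceed rule

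*Combined protocol and SAP*

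**What the plan says.** Section 3 gives the proceed rule: "The study will proceed to group 2 if there are not more than 2 vaccine-associated solicited AEs and no vaccine-associated LRIs" in seropositive children. The Protocol Summary, under Table 1, repeats it with time windows (Days 0-10 for solicited AEs, Days 0-28 for LRIs). Section 8.1.1 and Appendix IV define solicited AEs as fever, URI, otitis media and LRI, all of them clinical illness.

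Shedding appears once in the gate, in an expansion clause: "If 3 or more RSV-seropositive children have respiratory or febrile illness that coincides with shedding of" more than 10^2.5 PFU by culture, a further 15 seropositive children are enrolled. The Protocol Summary adds that the vaccine is then evaluated in an "additional 15 RSV-seropositive children before determining whether to continue with group 2".

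Section 1.4 says that a main purpose is to learn whether the virus is "well tolerated and restricted in replication in RSV-seropositive children". Section 9.2.1 lists among the primary infectivity outcomes "Peak titer of vaccine virus shed from Study Days 0-10 for RSV-seropositive" participants.

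The background describes how attenuation was judged before. In Section 1.2.1.1, rA2cpΔNS2 at 10^5.0 PFU "was shed by 3 of 8 vaccinated seropositive children with mean peak titers of" 10^3.4 PFU/mL, two more children were PCR-positive, and the virus "was deemed under-attenuated, and was not further evaluated in seronegative children". RSV ΔNS2/Δ1313/I1314L was given to 10 seropositive vaccinees at 10^6 PFU; no shedding was detected, and this was read as a sign of attenuation.

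**The concern.** Group 1 is the step before RSV-naive infants from 6 months of age receive a replicating virus that is new to humans. It is meant to show two things: that the vaccine is tolerated, and that its replication is restricted. The gate tests only the first. Peak titer is measured in every Group 1 child, but by itself it decides nothing about Group 2.

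If the virus replicated freely in seropositive children without making them ill, the rule as written would open Group 2. Prior immunity could plausibly mask illness in these children, and that protection is absent in Group 2. Section 3 itself notes that earlier live-attenuated RSV vaccines were far less restricted in children with titers below 1:40.

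**Working it through.** The plan states no operating characteristics for this gate, so there is no figure of its own to reproduce for the rule. The check is one of logic, followed by an illustration.

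**1. The rule applied to one case.** Suppose all 10 Group 1 vaccinees shed more than 10^2.5 PFU and none is ill.

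| Criterion | Count | Limit | Result |
|---|---|---|---|
| Vaccine-associated solicited AEs | 0 | no more than 2 | met |
| Vaccine-associated LRIs | 0 | 0 | met |
| Children both ill and shedding above cutoff | 0 | 3 or more triggers expansion | not triggered |

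The study proceeds. This step needs no assumption about rates.

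**2. Other rules that might catch it.**
- Section 8.3, stopping criteria 2 and 4: both require illness together with shedding.
- Section 8.3, criterion 5: covers laboratory patterns that the protocol team considers a significant safety issue. It is discretionary and names no shedding limit.
- Section 9.4.2: routine DSMB review covers completeness, adherence and AE data, with safety data pooled across arms. Section 7.1.4 adds as-needed review of study data.
- Sections 7.1.2 and 7.1.3: a sponsor safety plan and a medical monitor. That plan is not among the documents.
- Section 2.1: the 70% infection limit concerns over-attenuation in seronegative children, the opposite direction.

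None of these, in the documents provided, requires a look at shedding in well children.

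**3. How likely is high shedding?** Two precedents point in different directions.
- rA2cpΔNS2: 3/8 = 37.5% shed, exact 95% CI 9-76%. The rate above the cutoff is not given. If the mean of the three peaks is 3.4 log10, at least one is 3.4 or higher, so between 1/8 and 3/8 exceeded 2.5 log10 (taking both in PFU/mL). Illness in these children is not reported.
- RSV ΔNS2/Δ1313/I1314L: 0/10 at 10^6 PFU. The exact 90% upper limit is 1 − 0.05^(1/10) = 0.26, which reproduces the 0-26% that Table 25 gives for 0 of 10. A true rate of 37.5% would give 0/10 with probability 0.625^10 = 0.9%.

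Section 1.2.2.2 says that this second virus differs from the study virus only in the L mutation. The study virus is expected to be slightly less attenuated (Section 1.2.3), so 0/10 is favorable but not a guarantee.

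**4. Illustration of a limit that ignores illness.** With n = 10 and true rate p above the cutoff,

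P(3 or more) = 1 − [(1−p)^10 + 10p(1−p)^9 + 45p²(1−p)^8].

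- p = 0.10: 1 − (0.349 + 0.387 + 0.194) = 0.07
- p = 0.20: 1 − (0.107 + 0.268 + 0.302) = 0.32
- p = 0.375: 1 − (0.009 + 0.055 + 0.147) = 0.79

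The present expansion clause replaces p by p × q, where q is the assumed share of shedders who are ill at the time. At p = 0.375 it triggers with probability 0 (q = 0), 0.06 (q = 0.25), 0.28 (q = 0.5) and 0.79 (q = 1). These figures describe that clause alone, not the whole gate.

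**5. Unit.** The cutoff is written in PFU, while earlier candidates are reported in PFU/mL of wash. Section 6.10.2 gives a wash of about 20 mL. If the cutoff meant total PFU with full recovery, 10^2.5 = 316 PFU, and 316/20 = 15.8 PFU/mL = 10^1.2. The two readings differ by log10(20) = 1.3.

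**The case against.** The strongest reply is that the scenario is unlikely and that judgement would catch it. The closest clinical relative was not shed by any of 10 seropositive vaccinees at twice this trial's Group 1 dose (10^6 against 10^5.7 PFU). The study virus "is expected to be more attenuated than the previously tested vaccine candidate" rA2cpΔNS2, the candidate that did shed. For the lot used in this trial, the mean monkey tracheal peak was 2.9 log10 against 4.1 for wild type, although the nasopharyngeal peak was 3.8 against 4.2. The Group 2 dose is one-fifth of the Group 1 dose (10^5.0 against 10^5.7 PFU). On the text, rA2cpΔNS2 was itself stopped without any numeric shedding gate being cited, so the program has acted on shedding by judgement before. Section 8.1.1 links insufficient attenuation to solicited illness, which gives illness-based gating a rationale. If shedders are ill, the AE and LRI limits can also hold the study, so the expansion clause alone understates protection in that case.

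All of this bears on likelihood, and it stands. It does not change what the rule says. The expected attenuation relative to rA2cpΔNS2 rests on preclinical data, and the comparisons shown (Table 2 and Tables 27-29) do not include that virus. Discretion remains available but is not required.

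A reader might infer that nobody would look at shedding before Group 2 opens. The documents do not support that: as-needed DSMB review, criterion 5 and the sponsor's safety plan all leave room for it, and the plan's content cannot be judged from here.

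**Conclusion.** The gap is real as a matter of rule logic: within the documents provided, high-titer shedding in well Group 1 vaccinees meets the proceed rule, and no other written rule requires that it be reviewed. This conclusion rests on no assumed rate.

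Its practical size is uncertain. The trigger rates depend on p and q, which the documents do not give for this virus. A reader might take 37.5% as the expected shedding rate. It is not: it comes from a different virus in 8 children, the rate above the cutoff may have been as low as 12.5%, and the nearest relative gave 0 of 10. Nor do the documents show that this virus is under-attenuated, or that 3 of 10 is the right limit. That limit would hold only 12% of the time at a true rate of 12.5%, so it is a choice for the sponsor to defend. What stands is the need for a mandatory review, a limit fixed in advance, and a stated unit. It is an inexpensive improvement to a first-in-human safety gate that should be made.

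**What to change.** Amend the gate in Section 3 and the Protocol Summary as follows.

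- Before Group 2 opens, the sponsor and the DSMB review culture shedding in all Group 1 vaccinees regardless of illness: the number shedding and each child's peak titer.
- Enrollment is held for DSMB review, not stopped, if a stated limit is met. The limit is fixed before the first Group 1 block is unblinded, because Section 6.3 allows codes to be released block by block.
- The sponsor chooses the limit and gives its hold probabilities. Three or more of 10 vaccinees above the existing 10^2.5 cutoff, ill or not, is one example.
- State whether the cutoff is PFU/mL of wash or total PFU.

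No new sampling is needed: washes on Days 3-7 and 10 and their quantification are already planned (Sections 6.5.1.1 and 6.10.2). The costs are that Group 1 titers must be ready before Group 2 starts, which could cause delay within the April-October enrollment window, and that a virus later judged acceptable may sometimes be held. With the example limit, such a hold occurs 7% of the time if the true rate is 10%, and 32% if it is 20%.

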## 4 STUDY POPULATION

Approximately 15 RSV-seropositive children  $\geq$  12 months to  $<$  60 months of age will be enrolled; 10 will receive a single dose of  $10^{5.7}$  PFU of vaccine and 5 will receive a single dose of placebo. Subsequently, 21 to 30 RSV-seronegative infants and children  $\geq$  6 months to  $<$  25 months of age will be enrolled in the study and will receive a single dose of either  $10^{5.0}$  PFU of vaccine or placebo in a 2:1 ratio. These numbers were chosen based upon experience with phase I evaluation of other live-attenuated respiratory virus candidate vaccines ([11,23,25](#)) and statistical considerations (Section 9).

Placebo recipients are needed in pediatric studies to distinguish the background respiratory and febrile illnesses that occur in infants and children from those attributable to study vaccine. These numbers were chosen based upon experience with phase I evaluation of other live-attenuated respiratory virus candidate vaccines ([11,23,25](#)) and statistical considerations (Section 9).

Infants and children will be selected for participation according to the described study-specific co-enrollment considerations; the recruitment, screening, and enrollment process; and participant retention and withdrawal or termination.

## **4.1 INCLUSION CRITERIA FOR RSV-SEROPOSITIVE CHILDREN**

Potential RSV-seropositive participants must meet all of the following inclusion criteria to be enrolled in this study:

- 4.1.1.  $\geq$  12 months of age and  $<$  60 months of age at the time of inoculation
- 4.1.2. Screening serum specimen for RSV-neutralizing antibody is obtained within the calendar year of inoculation
- 4.1.3. Seropositive for RSV antibody, defined as serum RSV-neutralizing antibody titer  $\geq$  1:40
- 4.1.4. Pre-inoculation serum sample for RSV-neutralizing antibody specimen is obtained no more than 56 days prior to inoculation
- 4.1.5. In good health based on review of the medical record, history, and physical examination at the time of inoculation
- 4.1.6. Received routine immunizations appropriate for age based on the Advisory Committee on Immunization Practices (ACIP) Recommended Immunization Schedule for Children and Adolescents Aged 18 Years or Younger
- 4.1.7. Growing normally for age as demonstrated on a standard growth chart and has a current height and weight above the 3rd percentile for age
- 4.1.8. Expected to be available for the duration of the study
- 4.1.9. Parent/guardian is willing and able to provide written informed consent

